	 1 to the studied product / au produit à l'essai  2 to the study procedures / aux procédures de l'essai  3 other, define / autre, préciser :  0 no relationship / sans relation
30. If, according to the sponsor, the SAE appears to be related to the studied product, the event is: si selon le promoteur, l'EIG paraît plutôt lié au produit à l'essai, l'événement indésirable est :	 1 expected / attendu  0 unexpected / inattendu
31. Sponsor comments / commentaires du promoteur	

VII. ADDITIONAL INFORMATION / INFORMATIONS COMPLEMENTAIRES

FOR ADDITIONAL INFORMATION / POUR COMPLEMENT D'INFORMATION:

Date of report / Date du rapport :	Signature / Signature :
------------------------------------	-------------------------

AE form

PARTIE I : 1ère documentation de l'événement <small>First documentation of the adverse event</small>	N°/ #	
1. Description de l'événement / Event description En cas de réaction cutanée, préciser sa localisation et si elle correspond à la zone d'application du produit testé / In case of cutaneous reaction, specify its localisation and if it corresponds to the product application area
		
	2. Date de début de l'événement <small>Event onset date</small>		3. Sévérité / severity	4. Photo des signes cliniques / Pictures of clinical signs
	    		 ₁ légère / mild  ₂ modérée / moderate  ₃ sévère / severe	 ₀ NON / NO  ₁ OUI / YES  ₃ NA*
	5. Actions entreprises vis-à-vis du produit étudié <small>Actions taken with the studied product</small>		6. Actions entreprises vis-à-vis de l'événement <small>Actions taken due to the event</small>	7. Événement Indésirable Grave (EIG) <small>Serious Adverse Event (SAE)</small>

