	 ₀ aucune / none  ₁ arrêt définitif / definitive interruption  ₂ arrêt transitoire / temporary interruption → Durée / Duration  ₃ diminution de la dose / dose decrease		 ₀ aucune / none  ₁ traitement correcteur / corrective treatment Compléter le tableau des traitements concomitants / Complete concomitant treatment form  ₂ autre, à spécifier / other, define : 	 ₀ NON / NO  ₁ OUI / YES Si "OUI", remplir un formulaire de déclaration d'EIG. If "YES", complete a SAE declaration Form.
	8. Délai entre l'événement et la dernière prise/application du produit étudié ? <small>Timeframe from the last product taken/application</small>		9. Relation de causalité avec le(s) produit(s) étudié(s) <small>Event relationship with the study product(s)</small>	10. Relation avec les procédures de l'étude <small>Event relationship with the study methods</small>
	 minutes/heures/jours <small>minutes /hours /days</small>		 ₀ oui / yes  ₁ non / no  ₂ possible / possible	 ₀ oui / yes  ₁ non / no  ₂ possible / possible
	11. Evolution / Outcome		12. Commentaires / Comments <small>(Intensité, antécédents... / Intensity, medical history...)</small>	
	 Non connue / Unknown  En cours* / ongoing * commentaire obligatoire / Compulsory comment → Remplir la partie II et/ou la partie III à la prochaine cinéétique  Guéri <small>Resolved</small>		Si EI en cours, évolution à ce jour / If AE ongoing, evolution this day:  ₁ amélioration / improved  ₂ pas de changement / unchanged  ₃ aggravation / worsened  ₄ perdu de vue / lost to follow-up	
	Date de guérison     			
	Durée Duration  (secondes/minutes/heures/jours) <small>Seconds /minutes /hours /days</small>			

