	Date du rapport/ Report Date :		Nom et signature / Name and signature :	

STOP : REMPLIR LES PARTIES CI-DESSOUS LORS DES PROCHAINES CINETIQUES UNIQUEMENT POUR LES EI EN COURS

PARTIE II : suivi <small>Follow up</small>	Evolution de l'EI à chaque cinéétique (amélioration ou aggravation) / Evolution of the adverse event Dater et parapher chaque commentaire / date and initial each comment.		

PARTIE III : Guérison ou fin d'étude / Event or study termination	REMPILER LA PARTIE III A LA GUERISON DE L'EI PRECEDEMMENT EN COURS OU A LA FIN DE L'ETUDE		
	Date de guérison <small>Event stop date</small>     	 EI toujours en cours à la fin de l'étude / AE ongoing at the study end Date de fin de l'étude : <small>Study stop date</small>     	
	Sujet perdu de vue  <small>Untraceable subject</small>	L'EI nécessite-t-il un suivi ? NON / NO  ₁ <small>Does this AE need a follow up?</small> OUI **/YES  ₂ si oui, date prévue pour le suivi ** : <small>The predictive date for the follow up</small>     	
Date du rapport / Report Date :	Nom et signature / Name and signature :		

*NA = Non applicable/ *Not applicable*Rappel des définitions en fin de CRF/ *Definitions at the CRF end*

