4.3 Derived variables

Source data	Derivation rule	Label	Format
Date of last use of study product, date of D0 visit	TRT_DUR_D=Date of last use of study product – date of D0 visit +1	Treatment duration in days	Numeric
Date of end of study, date of selection visit	STUDY_DUR_D=Date of end of study – date of selection visit +1	Study duration in days	Numeric
OSDI total score	IF 0<=OSDI total score < 13 THEN OSDI_CL_D=1 IF 13<= OSDI total score < 23 THEN OSDI_CL_D=2 IF 23<= OSDI total score < 33 THEN OSDI_CL_D=3 IF 33<= OSDI total score < 100 THEN OSDI_CL_D=4	OSDI score in class	1 = "OSDI none" 2 = "OSDI Mild" 3 = "OSDI moderate" 4 = "OSDI severe"
Total Oxford score of the examined eye (i.e. worse eye defined at D0) at day 0, Total Oxford score of the corresponding eye at day 35 (i.e. day 84)	EVOL_OX_D0D35 (i.e. D84) = Total Oxford score of the examined eye (i.e. worse eye defined at D0) at day 35 (i.e. day 84) - Total Oxford score of the corresponding eye at day 0	Change of the Oxford total score from baseline to day 35 (i.e. day 84)	Numeric
Same derivation rule as above for changes on OSDI total score, Van Bijsterveld total score, Schirmer test result, TBUT total score, all ocular dryness symptoms score from D0 to D35 and from D0 to D84.			

Total Oxford score of the examined eye (i.e. worse eye defined at D0) at day 0, Total Oxford score of the corresponding eye at day 35 (i.e. day 84)	EVOL_OXREL_D0D35 (i.e. D84) = (Total Oxford score of the examined eye (i.e. worse eye defined at D0) at day 35 (i.e. day 84) - Total Oxford score of the corresponding eye at day 0) / Total Oxford score of the corresponding eye at day 0	Relative change of the Oxford total score from baseline to day 35 (i.e. day 84) in percentage	Numeric
Same derivation rule as above for changes (relative variation) on OSDI total score, Van Bijsterveld total score, Schirmer test result, TBUT total score, all ocular dryness symptoms score from D0 to D35 and from D0 to D84.			
Adverse Event	IF at least one adverse event is reported for the patient, ALO_AE=1 ELSE, ALO_AE=0	At least one AE	0 = "No" 1 = "Yes"
Same derivation rule as above for at least one TEAE, at least one severe AE, at least one AE related to the treatment, at least one SAE, at least one AE that lead to study withdrawal			

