7.7.1 Adverse events

The adverse events will be coded using the MedDRA dictionary. All Adverse events will be presented by System Organ Class and Preferred Term.

Treatment-emergent AEs (TEAEs) will be defined as AEs with onset date on or after the first day of the study product instillation. If the AE onset date is not available, AEs will be considered as TEAEs by default.

The number and percentage of patients experiencing at least one AE will be provided by treatment group, by primary SOC and PT, for the following categories of events:

- All AEs
- All TEAEs
- Maximum severity for all events by PT (regardless of causality)
- Treatment-related AEs
- Serious AEs
- AEs that lead to study withdrawal.

The difference between treatments groups on the incidence rate will be analysed for each PT using Fisher's exact test.

The statistical significance level of 5% will be applied for the safety analyses.

Will be described globally and by treatment groups (the ocular TEAEs and the non-ocular TEAEs will be analysed separately):

Total number of AEs:

- All AEs
- All TEAEs
- All AEs by severity
- AEs by relationship to the treatment
- AEs by seriousness criterion
- AEs that lead to study withdrawal.

Number and percentage of patients who has presented at least one AE:

- At least one AE
- At least one TEAE
- At least one severe AE
- At least one AE related to the treatment
- At least one SAE
- At least one AE that lead to study withdrawal.

The difference between treatments groups on the incidence rate will be analysed for each PT using Fisher's exact test.

The statistical significance level of 5% will be applied for the safety analyses.

An individual data listing of all AEs will be given. With following information: centre number / patient number / treatment group / inclusion date (D0) / age / sex / AE number / AE description / SOC / PT / Time of occurrence* / Duration** (start date / end date) / severity / picture of clinical signs / Actions taken / Seriousness criterion / timeframe from the last product use-application / relationship with the study product / relationship with the study method / outcome / comments.

The same listing will be produced for SAEs.

* Time of occurrence will be derived in days as follow: inclusion date (D0) – AE start date

** duration in days will be derived as follow: end date – start date +1

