Evaluation of performance by the investigator at D0, D35 and D84 by treatment groups – PP population

Evaluation of performance by the investigator at D0, D35 and D84 by treatment groups – ITT population

Frequency of use of the product at D0, D35 and D84 by treatment groups – PP population

Frequency of use of the product at D0, D35 and D84 by treatment groups – ITT population

AEs by SOC, PT and by treatment groups – Safety Population
TEAEs by SOC, PT and by treatment groups – Safety Population
Severe AEs by SOC, PT and by treatment groups – Safety Population
Treatment-related AEs by SOC, PT and by treatment groups – Safety Population
Serious AEs by SOC, PT and by treatment groups – Safety Population
AEs that lead to study withdrawal by SOC, PT and by treatment groups – Safety Population

AEs by severity and treatment groups
AEs by relationship to the treatment and treatment groups
AEs by seriousness criterion and treatment groups

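### The AE form grades severity only at first documentation, so a non-serious event that worsens later may be counted at its first grade in the severity summaries

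*SAP*

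**What the plan says.** **Analysis.** SAP 7.7.1 (like protocol 7.1.3) lists "Maximum severity for all events by PT (regardless of causality" among the categories for which patients are counted by SOC and PT. SAP 7.7.1 also plans counts of AEs by severity and of patients with a severe AE. SAP 4.3 derives yes/no flags that include "at least one severe AE, at least one AE related to the treatment". SAP 9.1 lists a table titled "Severe AEs by SOC, PT and by treatment groups – Safety Population". None of these sections names the source field or says whether the grade is the first, the current or the worst.

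**Data capture.** On the AE form in protocol Appendix 1, Part I is headed "First documentation of the adverse event". It contains box "3. Sévérité / severity", with the options mild, moderate and severe, and ends with its own report date and signature. A stop line then directs staff to complete the parts below it at later time points, for ongoing events only. Part II takes dated and initialled remarks ("amélioration ou aggravation) / Evolution of the adverse event"). Part III takes the end date, whether the event is still ongoing, loss to follow-up and the need for further follow-up.

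**Definition.** Protocol 14.1.8 defines severity as the intensity of the event on three levels. It does not say at which moment of the event the level is assigned.

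**The concern.** The summaries need the highest grade an event reached. The form asks for a grade once, when the event is first written down, and sends later worsening to a free-text area. If staff follow the form as printed, an event that worsens within itself keeps its first grade, and the analyst has no coded value from which to recover the peak.

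Safety over 84 days is a stated secondary objective. The post-dose visits are D35 and D84, so an event first documented at D35 and still ongoing has nominally 84 − 35 = 49 days, or seven weeks, in which it can change. Any grade lost this way is lost in one direction, towards milder. The severe-AE counts are where a reader would look for poorly tolerated product use.

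**Working it through.** This is a question of data capture, so the check sets the form beside the outputs that depend on it.

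1. **Where a grade is coded on the AE form.** Part I, box 3: yes. Part II: no. Part III: no. There is one grade per event, placed at first documentation.

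2. **Other fields that bear on intensity.** Box 11 in Part I ("If AE ongoing, evolution this day") has options for improved, unchanged, worsened and lost to follow-up. That is a direction, not a grade, and it refers to the day Part I is completed. Box 12 in Part I prompts for remarks ("Intensity, medical history"), again as free text. Part II remarks can describe worsening but are not graded.

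3. **What each output needs.**
   - Maximum severity by PT, for a patient with several separate events of the same PT: the highest box 3 value. This can be derived.
   - Maximum severity by PT, for a single event that worsens: the peak grade. This is not on the form unless box 3 is changed.
   - Severe-AE flag and AEs by severity: one grade per event. They are correct only if box 3 holds the worst grade.

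4. **One record traced through.** Suppose burning is first documented at D35 as mild and is ongoing. At D84 the Part II remark says it has worsened and now prevents usual activity, which protocol 14.1.8 classes as severe. With box 3 unchanged, the event counts as mild and, absent another severe event, the patient's severe-AE flag is 0. With box 3 updated, the event counts as severe and the flag is 1.

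5. **Does the SAE form close the gap?** It has its own severity item and can be filed as an initial or a follow-up report, so a serious event can be graded again. But severe and serious are different things: being unable to work or carry out usual activity (14.1.8) need not meet any seriousness criterion in 14.1.4. The SAP also does not say which form feeds the tables when both exist.

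6. **Size.** The documents give no AE rate and no rate of worsening, so no count can be derived. As a conversion only: with 40 patients randomised per arm (protocol 6.3.6), and if all enter the Safety population, each patient whose flag should be 1 but is 0 lowers that arm's severe-AE proportion by 1/40 = 2.5 percentage points.

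**The case against.** The strongest reply is that nothing freezes the first grade. Box 3 is labelled severity, not initial severity. Protocol 8.1.2 allows changes to e-CRF data if they are dated, initialled and explained. Protocol 8.1.3.1 plans e-CRF specifications and completion guidelines, which are not among the documents and are a natural place for a worst-grade instruction. The printed form also looks generic (box 1 asks about skin reactions), so the live e-CRF may differ. An event that peaked before it was first reported can be graded at its peak in Part I. Worsening leaves some trace in boxes 11 and 12 and in Part II, and the AE listing in SAP 7.7.1 shows outcome and comments beside severity.

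Much of this stands, and it limits the point to a risk. It does not remove it. Permission to change a field is not an instruction to do so, and the form itself sends worsening elsewhere. The guidelines might close the gap, but nothing in the protocol or SAP requires them to. A free-text trace lets a reader notice worsening but does not supply a grade to the tables.

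Two stronger readings are tempting. A reader might infer that every worsening event will be tabulated as mild. The documents do not say so, because box 3 can be changed and serious events can be re-graded. A reader might also infer that the loss favours DM05. No data on worsening by arm are given. The minor toxicity signs in protocol 3.1.1 came from an ex vivo test under hourly dosing that the protocol itself calls unrepresentative, and protocol 14.6 describes anticipated effects as very rare and transient.

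**Conclusion.** The point holds as a gap between the form and the analysis. As printed, the AE form has no coded place for a grade reached after first documentation, and neither document defines severity as the worst grade. A non-serious event that worsens within itself may therefore be under-graded in the maximum-severity summary, the AEs by severity and the severe-AE flag, unless box 3 is overwritten.

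The conclusion assumes that the e-CRF follows the Appendix 1 form and that the completion guidelines give no worst-grade instruction; either could be otherwise. The reach is limited. Highest grades across separate events of one PT, serious events with a follow-up SAE report, and events already at their peak when first documented are not affected. The outputs are safety summaries, and the primary analysis does not depend on them. It is still worth correcting, because a grade that was never collected cannot be rebuilt at analysis.

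**What to change.** - **Form or e-CRF.** Add a dated field for the worst severity reached (mild, moderate, severe) to Parts II and III. Alternatively, state in protocol 14.1.8 and in the completion guidelines that box 3 is updated to the worst grade, with audit trail.
- **SAP 4.3 and 7.7.1.** Derive maximum severity, the severe-AE flag and AEs by severity from that worst grade. State whether the AE form or the SAE form prevails when they differ.
- **Events already collected.** Where box 11 shows worsening or a Part II remark describes it, query the blinded investigator for the worst grade before database lock. The data review should not assign grades from the remarks: under protocol 8.1.3.2 its required attendees are the sponsor, the project manager, the statistician and the monitor, with the coordinating investigator optional, and 14.1.8 makes severity a clinical determination.

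The cost is one field, a short SAP addition and a few queries. Severe-AE counts may come out slightly higher.

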8 REPORTING CONVENTIONS

8.1 Software used

Statistical analysis will be made using SAS® GUIDE software (version 9.4). Tables results will be computed with SAS® GUIDE software (version 9.4). Figures will be created using Microsoft® Excel or SAS®GUIDE version 9.4.

8.2 General considerations

All p-values will be rounded to 3 decimal places. If a rounded p-value is 0.000 (i.e., the actual p-value is less than 0.0005), then this will be presented as a p-value of “<0.001”.

All date fields will be presented in a format of ddmm/yyyy (e.g., 01Jan2004) in the listings.

8.3 Statistical summary conventions

For tables, sample sizes for each treatment group will be presented as totals in the column header (N=xxx), where appropriate. Sample sizes shown with summary statistics are the number (n) of patients with non-missing values.

Summaries for categorical variables will include only categories that patients had a response in. Percentages corresponding to null categories (cells) will be suppressed. All summaries for continuous variables will include: N, mean, and SD. Other summaries (e.g. median, quartiles, 5%, 95% intervals) will be used as appropriate. All percentages should be rounded and reported to a single decimal place (xx.x%). If percentages are reported as integers, percentages greater than 0% but <1% will be reported as <1%, whereas percentages greater than 99% but <100% will be reported as >99%. A percentage of 100% will be reported as 100%. No value of 0% should be reported. Any computation of percent that results in 0% is to be reported as a blank.

8.4 Examples of tables, listings and figures

8.4.1 Quantitative variables:

Table xx: Description of quantitative variables

		Group A N=xxx	Group B N=xxx	Total N=xxx	p-value
Variable 1	N	x	x	x	
	Missing	x	x	x	
	Mean \pm SD	xx.xx \pm xx.xx	xx.xx \pm xx.xx	xx.xx \pm xx.xx	
	Median	xx.xx	xx.xx	xx.xx	
	Q1 ; Q3	xx.xx ; xx.xx	xx.xx ; xx.xx	xx.xx ; xx.xx	
	Min. ; Max.	xx.xx ; xx.xx	xx.xx ; xx.xx	xx.xx ; xx.xx	
Variable 2	N	x	x	x	
	Missing	x	x	x	
	Mean \pm SD	xx.xx \pm xx.xx	xx.xx \pm xx.xx	xx.xx \pm xx.xx	
	Median	xx.xx	xx.xx	xx.xx	
	Q1 ; Q3	xx.xx ; xx.xx	xx.xx ; xx.xx	xx.xx ; xx.xx	
	Min. ; Max.	xx.xx ; xx.xx	xx.xx ; xx.xx	xx.xx ; xx.xx	

95% Confidence Intervals might be presented in the tables.

8.4.2 Qualitative variables:

Table xx: Description of qualitative variables

		Group A N=xxx	Group B N=xxx	Total N=xxx	p-value
Variable 1	N	x	x	x	x
	Missing	x	x	x	x
	Modality 1	xx (xx.x%)	xx (xx.x%)	xx (xx.x%)	xx (xx.x%)
	Modality 2	xx (xx.x%)	xx (xx.x%)	xx (xx.x%)	xx (xx.x%)
Variable 2	N	x	x	x	x
	Missing	x	x	x	x
	Modality 1	xx (xx.x%)	xx (xx.x%)	xx (xx.x%)	xx (xx.x%)
	Modality 2	xx (xx.x%)	xx (xx.x%)	xx (xx.x%)	xx (xx.x%)

95% Confidence Intervals might be presented in the tables.

8.4.3 Adverse Events:**Table xx: AEs description by SOC and PT**

SOC and PT	Total (N=xxx)		
	AE (1)	n (2)	% (3)
TOTAL	XX	XX	XX.X
SOC 1	XX	XX	XX.X
SOC 1 – PT 1	XX	XX	XX.X
SOC 1 – PT 2	XX	XX	XX.X
....	XX	XX	XX.X
SOC 2	XX	XX	XX.X
SOC 2 – PT 1	XX	XX	XX.X
SOC 2 – PT 2	XX	XX	XX.X
....	XX	XX	XX.X

(1) Number of AEs

(2) Number of subjects with at least one AE

(3) % of subjects with at least one AE

Table xx: AE by SOC, PT and by treatment group

SOC and PT	DM05 (N=xxx)			Optive® (N=xxx)			Total (N=xxx)		
	AE (1)	n (2)	% (3)	AE (1)	n (2)	% (3)	AE (1)	n (2)	% (3)
TOTAL	XX	XX	XX.X	XX	XX	XX.X	XX	XX	XX.X
SOC 1	XX	XX	XX.X	XX	XX	XX.X	XX	XX	XX.X
SOC 1 – PT 1	XX	XX	XX.X	XX	XX	XX.X	XX	XX	XX.X
SOC 1 – PT 2	XX	XX	XX.X	XX	XX	XX.X	XX	XX	XX.X
....	XX	XX	XX.X	XX	XX	XX.X	XX	XX	XX.X
SOC 2	XX	XX	XX.X	XX	XX	XX.X	XX	XX	XX.X
SOC 2 – PT 1	XX	XX	XX.X	XX	XX	XX.X	XX	XX	XX.X
SOC 2 – PT 2	XX	XX	XX.X	XX	XX	XX.X	XX	XX	XX.X
....	XX	XX	XX.X	XX	XX	XX.X	XX	XX	XX.X

(1) Number of AEs

(2) Number of subjects with at least one AE

(3) % of subjects with at least one AE

9 TABLES, LISTING AND FIGURES

Planned tables, listing and figures are for information purposes, and are subject to change.

9.1 Planned tables

Subjects with at least one major/minor deviations

Protocol deviations

Analysis populations

Number of active centre

Number of included and randomized patients

Number of included and randomized patients by treatment groups

Number of included and randomized patients by centre

Course of the study

Number of patients having finished the study normally by treatment groups.

Reason of withdrawal

Study follow-up

Normal study end

Demographic data by treatment groups – PP population

Demographic data by PP/ITT population

Contraception (for female only) by treatment groups – PP population

Contraception (for female only) by PP/ITT population

Medical history at selection visit by treatment groups – PP population

Medical history at selection visit by PP/ITT population

Product and document dispensation by treatment groups – PP population

Product and document dispensation by PP/ITT population

Ocular surface disease index (OSDI) at selection visit by treatment groups – PP population

Ocular surface disease index (OSDI) at selection visit by PP/ITT population

Ocular surface disease index (OSDI) at D0 visit by treatment groups – PP population

Ocular surface disease index (OSDI) at D0 visit by PP/ITT population

Corneal fluorescent staining (Oxford scale) at selection visit by treatment groups – PP population

Corneal fluorescent staining (Oxford scale) at selection visit by PP/ITT population

Corneal fluorescent staining (Oxford scale) at D0 visit by treatment groups – PP population

Corneal fluorescent staining (Oxford scale) at D0 visit by PP/ITT population

Tear film Break Up Time (TBUT) at selection visit by treatment groups – PP population

Tear film Break Up Time (TBUT) at selection visit by PP/ITT population

Tear film Break Up Time (TBUT) at D0 visit by treatment groups – PP population

Tear film Break Up Time (TBUT) at D0 visit by PP/ITT population

Schirmer test at selection visit by treatment groups – PP population

Schirmer test at selection visit by PP/ITT population

Schirmer test at D0 visit by treatment groups – PP population

Schirmer test at D0 visit by PP/ITT population

Pregnancy test (women with childbearing potential only – D0 visit) by treatment groups – PP population

Pregnancy test (women with childbearing potential only – D0 visit) by PP/ITT population

Definition of the worse eye (D0 visit) by treatment groups – PP population

Definition of the worse eye (D0 visit) by PP/ITT population

Previous and concomitant medication - ITT population

Product and document dispensation at D35 by treatment groups – ITT population

Product and document dispensation at D84 by treatment groups – ITT population

Pregnancy test (women with childbearing potential only – D84) by treatment groups – ITT population

Oxford scores on the worse eye at D0 by treatment groups – ITT population

Oxford scores on the worse eye at D0 by treatment groups – PP population

Oxford scores on the worse eye at D35 by treatment groups – ITT population

Oxford scores on the worse eye at D35 by treatment groups – PP population

Change from D0 to D35 of the Oxford total score on the worse eye by treatment groups – ITT population

Change from D0 to D35 of the Oxford total score on the worse eye by treatment groups – PP population

Results of the non-inferiority analysis (main analysis) – PP population

Results of the superiority analysis (main analysis) – ITT population

Results of the superiority analysis (main analysis) – PP population

Results of the non-inferiority analysis (sensitivity analysis n°1) – PP population

Results of the non-inferiority analysis (sensitivity analysis n°1) – ITT population

Results of the non-inferiority analysis (sensitivity analysis n°2) – PP population

Results of the non-inferiority analysis (sensitivity analysis n°2) – ITT population

For Oxford total score on worse eye, OSDI total score, Van Bijsterveld total score, Schirmer test result on worse eye, TBUT total score on worse eye, all ocular dryness symptoms score separately and then globally (total score):

Description of the parameter at D0, D35 and D84 by treatment groups – PP population

Description of the parameter at D0, D35 and D84 by treatment groups – ITT population

Description of the change of the parameter from D0 to D35 and from D0 to D84 by treatment groups - PP population

Description of the change of the parameter from D0 to D35 and from D0 to D84 - ITT population

Results of the ANOVA model for the parameter – PP population

Results of the ANOVA model for the parameter – ITT population

OSDI in class at D0, D35 and D84 by treatment groups – PP population

OSDI in class at D0, D35 and D84 by treatment groups – ITT population

Evaluation of performance by the patient at D0, D35 and D84 by treatment groups – PP population

Evaluation of performance by the patient at D0, D35 and D84 by treatment groups – ITT population

Evaluation of performance by the investigator at D0, D35 and D84 by treatment groups – PP population

Evaluation of performance by the investigator at D0, D35 and D84 by treatment groups – ITT population

Frequency of use of the product at D0, D35 and D84 by treatment groups – PP population

Frequency of use of the product at D0, D35 and D84 by treatment groups – ITT population

AEs by SOC, PT and by treatment groups – Safety Population
TEAEs by SOC, PT and by treatment groups – Safety Population
Severe AEs by SOC, PT and by treatment groups – Safety Population
Treatment-related AEs by SOC, PT and by treatment groups – Safety Population
Serious AEs by SOC, PT and by treatment groups – Safety Population
AEs that lead to study withdrawal by SOC, PT and by treatment groups – Safety Population

AEs by severity and treatment groups
AEs by relationship to the treatment and treatment groups
AEs by seriousness criterion and treatment groups

